2.8.1.1 Adverse events of special interest / grouping of AEs

Allergic dermatitis, elevation in hepatic enzymes and neutropenia are the potential risks related to EMA401. Dizziness, headache, nausea, pre syncope and upper respiratory tract infections are the expected events related to EMA401. In addition suicidality and drug abuse related events will be adverse events of special interest. The search criterion for each of these risks and events will be defined based on MedDRA and on the Program Compound Case Retrieval Sheet.

The most recent Compound Case Retrieval Strategy (eCRS) at the time of database lock will be used to determine the MedDRA search criteria to identify events of special interests.

2.8.2 Deaths

The primary reason for death will be summarized by system organ class and preferred term. All deaths will be listed. Deaths for screen failures will be listed separately.

2.8.3 Laboratory data

The summary of laboratory evaluations will be presented for three groups of laboratory tests: Hematology, Chemistry and Urinalysis.

The number and percentage of patients with newly occurring or worsening laboratory abnormalities meeting the clinically notable criteria at any post-baseline visit will be summarized by laboratory parameter. For a patient to meet the criterion of a newly occurring clinically notable value, the patient needs to have a baseline value that is not clinically notable for that parameter. For a patient to meet the criterion of a worsening clinically notable value, the patient needs to have a baseline value that is clinically notable and also have a worse post-baseline value. For patients with missing baseline value, any post-baseline notable value will be considered as newly occurring.

Incidence of newly occurring liver enzymes abnormalities and renal events will be summarized using the number and percentage of patients by treatment group. Notable laboratory values will be listed.

Laboratory assessments performed at the follow-up visits in the scope of the USM will not be included in the summaries but will be listed. That means, assessments reported 21 days after end of study date will not be included in the summary tables.

Liver function tests (LFT)

To evaluate potential drug-induced liver injury, the number and percentage of patients with newly occurring or worsening abnormalities in liver function tests at any time post-baseline will be summarized by treatment. The same approach as for notable laboratory values will be used to define newly occurring or worsening abnormalities in liver function tests.

When a criterion contains multiple laboratory parameters, the criterion will only be considered to have been met when all conditions occur at the same time (i.e., within the same sample). A case where all criteria are met at a post-baseline time point will be considered as newly occurring if the criteria are not met at baseline and will be considered as worsening if the criteria are met at baseline and at least one component is worsening from baseline irrespective of whether the other(s) are better.

Listings of patients with clinically notable LFT values will be provided.

The same analysis will be repeated for the Treatment withdrawal epoch.

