6.5.4.1 Hematology

The following parameters will be collected: standard hematology with differential (red blood cell count, white blood cell count, platelet count, hemoglobin, hematocrit, mean corpuscular volume (MCV), mean corpuscular hemoglobin (MCH), mean corpuscular hemoglobin concentration (MCHC), red blood cell morphology, white blood cell differential).

Measures of coagulability to be collected: activated partial thromboplastin time (aPTT), prothrombin time/International Normalized Ratio (PT/INR)

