Weight	Baseline weight (kg)	and an and a	increase of $\geq 7\%$ decrease of $\geq 7\%$

bpm= beats per minute

Clinically notable laboratory values

Notable laboratory values will be specified in the laboratory manual with specific alert values. Both the Novartis clinical team and the investigator will be notified for all types of alerts.

14 Appendix 2: Liver event and Laboratory trigger Definitions and Follow-up Requirements

Table 14-1 Liver Event and Laboratory Trigger Definitions

	Definition/ threshold
LIVER LABORATORY TRIGGERS	
 • $3 \times \text{ULN} < \text{ALT} / \text{AST} \leq 5 \times \text{ULN}$ • $1.5 \times \text{ULN} < \text{TBL} \leq 2 \times \text{ULN}$
LIVER EVENTS	
 • ALT or $\text{AST} > 5 \times \text{ULN}$ • $\text{ALP} > 2 \times \text{ULN}$ (in the absence of known bone pathology) • $\text{TBL} > 2 \times \text{ULN}$ (in the absence of known Gilbert syndrome) • ALT or $\text{AST} > 3 \times \text{ULN}$ and $\text{INR} > 1.5$ • Potential Hy's Law cases (defined as ALT or $\text{AST} > 3 \times \text{ULN}$ and $\text{TBL} > 2 \times \text{ULN}$ [mainly conjugated fraction] without notable increase in ALP to $> 2 \times \text{ULN}$) • Any clinical event of jaundice (or equivalent term) • ALT or $\text{AST} > 3 \times \text{ULN}$ accompanied by (general) malaise, fatigue, abdominal pain, nausea, or vomiting, or rash with eosinophilia • Any adverse event potentially indicative of a liver toxicity*

*These events cover the following: hepatic failure, fibrosis and cirrhosis, and other liver damage-related conditions; the non-infectious hepatitis; the benign, malignant and unspecified liver neoplasms
TBL: total bilirubin; ULN: upper limit of normal

Table 14-2 Follow Up Requirements for Liver Events and Laboratory Triggers

Criteria	Actions required	Follow-up monitoring
Potential Hy's Law case ^a	
 • Discontinue the study treatment immediately • Hospitalize, if clinically appropriate • Establish causality • Complete liver CRF 	ALT, AST, TBL, Alb, PT/INR, ALP and γGT until resolution ^c (frequency at investigator discretion) 

ALT or AST		

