The planned sample size allows to estimate the placebo-corrected response (the treatment difference between the active EMA401 doses and placebo) with a root mean squared error of 0.34 averaged over the three active doses and taking the maximum over the 5 candidate models.

4 Change to protocol specified analyses

An additional population, the mFAS population, has been defined.

The following analyses were specified in the protocol but will not be performed due the early termination of study:

- first and third supplementary analysis to the primary analysis
- tipping point analysis
- supplementary responder analyses
- ANCOVA analyses for BPI-SF, worst NRS pain score, ISI
- Proportional odds model for PGIC
- Apart from analyses of clinical abnormalities summaries of laboratory data, vital signs and ECG intervals have been removed.
- Shift tables of laboratory data
- No safety figures will be presented
- Bazett correction for QTc
- time to "sustained" pain reduction

The following analyses have been added:

- sensitivity analyses on modified full analysis population
- analyses of TEAEs with onset before study termination date

The analyses of patient disposition for the treatment and treatment withdrawal epoch will be based on the FAS population only.

Analyses of duration of exposure to study treatment will be based on the SAF population only.

5 Appendix

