5.3 Laboratory parameters derivations

Liver events defined by laboratory parameter abnormalities (additional non-lab criteria as provided in the protocol are covered under the adverse events analysis, safety topics of interest):

- ALT or $AST > 5 \times ULN$
- $ALP > 2 \times ULN$
- $TBL > 2 \times ULN$
- ALT or $AST > 3 \times ULN$ and $INR > 1.5$
- ALT or $AST > 3 \times ULN$ and $TBL > 2 \times ULN$ AND $ALP \leq 2 \times ULN$ (Potential Hy's Law cases)

- ALT or AST > 3 × ULN

Renal events defined by laboratory parameter abnormalities (additional non-lab criteria as provided in the protocol are ignored):

- Serum creatinine increase 25 – 49% compared to baseline
- Serum creatinine increase ≥ 50% compared to baseline
- New dipstick proteinuria ≥1+
- New dipstick glycosuria ≥1+ not due to diabetes
- New dipstick hematuria ≥1+ not due to trauma
- Albumin- or Protein-creatinine ratio increase ≥2-fold
- Albumin-creatinine ratio (ACR) ≥30 mg/g or ≥3 mg/mmol
- Protein-creatinine ratio (PCR) ≥150 mg/g or >15 mg/mmol

Laboratory results will be reported in SI units.

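### The SAP counts a combined liver case only when every component is abnormal in one sample, so a patient whose bilirubin or INR crosses its limit only after ALT/AST has fallen to 3 x ULN or below is missing from the combined row

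*SAP*

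**What the plan says.** SAP 2.8.3 summarizes, by treatment, the patients with new or worsening liver test abnormalities at any time after baseline. For a criterion made of several parameters it adds a timing rule: "the criterion will only be considered to have been met when all conditions occur at the same time (i.e., within the same sample".

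SAP 5.3 contains two such criteria:
- The first joins transaminases with bilirubin and ALP: "ALT or $AST > 3 \times ULN$ and $TBL > 2 \times ULN$ AND $ALP \leq 2 \times ULN$ (Potential Hy's Law cases".
- The second joins transaminases with coagulation: "ALT or $AST > 3 \times ULN$ and $INR > 1.5".

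The same section also has single-parameter rows for ALT or AST > 3 x ULN, ALT or AST > 5 x ULN, ALP > 2 x ULN and total bilirubin (TBL) > 2 x ULN. It has no row for INR alone.

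Protocol Table 14-1 defines both combined events with the same limits. Its Hy's Law entry qualifies the bilirubin and ALP parts ("mainly conjugated fraction] without notable increase in ALP to" a level above twice the upper limit) but says nothing about timing. Footnote a to Table 14-2 is also silent on timing.

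SAP 2.8.1.1 names the risk: "Allergic dermatitis, elevation in hepatic enzymes and neutropenia are the potential risks related to EMA401". SAP Section 4 drops shift tables and all laboratory summaries other than those of clinical abnormalities, and adds: "No safety figures will be presented". The same-sample rule is not in that section's list of changes.

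**The concern.** The components of one liver episode need not be abnormal on the same day. Table 14-2 has study treatment stopped at several ALT/AST criteria, with ALT, AST, TBL, ALP and INR then followed to resolution at a frequency the investigator chooses. Protocol 7.3 lets repeats be run locally when the central laboratory cannot be used. Scheduled chemistry in Table 6-1 is one to two weeks apart. ALT/AST may therefore be at or below 3 x ULN in the sample where TBL or INR first exceeds its limit. Under the SAP rule that patient is absent from the combined row.

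Combined cases are rare, so one case more or less changes how the table reads. The displays that might have shown the sequence have been removed. Listings of notable values remain, but they give no count of combined cases by treatment.

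The wording raises a second, smaller point. INR is listed under Hematology ("Measures of coagulability to be collected: activated partial thromboplastin time (aPTT), prothrombin time/International Normalized Ratio (PT/INR", Protocol 6.5.4.1), while ALT, AST, TBL and ALP are in the chemistry panel (6.5.4.2). The word sample leaves it unclear whether an ALT value and an INR value from one visit count as concurrent.

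**Working it through.** The plan gives no figure to reproduce, and the documents contain no liver results. The check applies the SAP criteria to four hypothetical patients, each with two samples (Day 29 and Day 43, the Week 4 and Week 6 visits). All laboratory values are assumptions. Values not shown are normal (TBL and ALP 1 x ULN, INR 1.0).

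The same-sample rule requires one sample that meets every component. The any-time rule requires each component to be met in some post-baseline sample, with ALP <= 2 x ULN throughout for Hy's Law.

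| Patient | Day 29 | Day 43 | Criterion | Same sample | Any time | Single-parameter rows met |
|---|---|---|---|---|---|---|
| A | ALT 4 x | ALT 4 x, TBL 2.5 x | Hy's Law | counted | counted | ALT > 3, TBL > 2 |
| B | ALT 6 x | ALT 2.5 x, TBL 2.5 x | Hy's Law | not counted | counted | ALT > 3, ALT > 5, TBL > 2 |
| C | ALT 4 x | ALT 3.5 x, INR 1.7 | ALT/INR | counted, if one draw is one sample | counted | ALT > 3 |
| D | ALT 6 x | ALT 2.5 x, INR 1.7 | ALT/INR | not counted | counted | ALT > 3, ALT > 5 |

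A and C show that a later rise is counted if ALT/AST is still above 3 x ULN when TBL or INR crosses its limit. B and D show the gap: the elevations never overlap in one sample. B stays visible in the TBL row. D leaves no INR signal in the SAP 5.3 rows, because there is no INR-alone row. The general table of notable values might show D's INR, but Protocol Appendix 1 leaves those limits to the laboratory manual.

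Size of one case:
- SAP Amendment 1 gives 129 patients randomized, and SAP 1.1 gives 1:1:1 allocation.
- Assuming equal arms, 129 / 3 = 43 per arm and 2 x 43 = 86 on EMA401.
- One case is 1/86 = 1.2% of EMA401 patients, or 1/43 = 2.3% of one arm.

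A combined row reading 0 in place of 1 would differ by these amounts.

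**The case against.** Counting concurrent values is a defensible and more specific choice. Tables 14-1 and 14-2 define events for monitoring, and their silence on timing does not prescribe non-concurrent counting. Protocol 9.5.2 leaves the detailed analysis of laboratory tests to the SAP. The rule applies to placebo as well. For ALT > 5 to <= 8 x ULN, Table 14-2 asks for a repeat within 48 hours and follow-up if the elevation persists, so real patients like B and D should have intermediate samples, which makes an overlap more likely to be caught. Liver events also lead to liver CRF pages and a causality assessment, and clinically significant hepatic values go to the DMC. All of this stands. It is why the concurrent row should stay and why the gap is narrow. It does not give a count by treatment of patients with no overlapping sample.

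A reader might draw three stronger conclusions, none of which the documents support:
- *Any patient whose TBL or INR rises after ALT is lost.* Patients A and C show otherwise.
- *The ALT/INR row can never be met, because the two tests sit in different panels.* SAP 2.8.3 goes on to apply the rule at a post-baseline time point, and Table 6-1 schedules hematology and blood chemistry in one row at the same visits. The wording needs clarifying, but the row can be met.
- *The trial was stopped for a liver reason, so this count carries the safety conclusion.* The documents give no reason for the urgent safety measures. They also do not single out the combined count: SAP 2.8.3 assigns the evaluation of drug-induced liver injury to liver test abnormalities as a whole.

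**Conclusion.** The point holds in a limited form. The SAP adds a timing condition that the protocol's definitions do not carry. Patients whose TBL or INR crosses its limit only after ALT/AST has fallen to 3 x ULN or below are left out of the combined rows. They are not lost altogether: a missed Hy's Law patient remains in the ALT/AST and TBL rows and in the listings, and a missed ALT/INR patient remains in the ALT/AST rows of SAP 5.3.

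The size cannot be estimated from the documents. One case would be 1.2% of EMA401 patients or 2.3% of an arm, assuming equal arms and that all randomized patients are in the safety population. Whether any such patient exists is unknown. This is a cheap improvement to a table for a named risk, and it does not show the liver analysis to be invalid.

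**What to change.** In SAP 2.8.3 and 5.3:
- Keep the concurrent row for each combined criterion, but replace *same sample* with *same collection date or time point*.
- Add a second row, by treatment, for patients who meet all components but not concurrently. Use either any post-baseline values or a prespecified window. The documents give no window, so a length such as 30 days must be stated as an assumption.
- For the non-concurrent Hy's Law row, state which ALP value is used. This too is an assumption.
- Include unscheduled repeats and the local liver tests recorded on the Liver CRF.
- State how the window works with two existing SAP rules: assessments reported 21 days after end of study are kept out of the summary tables (2.8.3), and the treatment and withdrawal periods are reported separately (2.8). Either could split one episode.
- List the change in SAP Section 4.

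The cost is SAP wording, one extra row for each of the two criteria, and narrative review of a few non-concurrent cases that may prove unrelated. Replacing the concurrent rule outright would trade specificity for sensitivity and is not needed. The change affects counting only, not patient management.

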2.8.4 Other safety data

2.8.4.1 ECG

The (uncorrected) QT interval will be corrected according to Fridericia’s formulae. The incidence rates of newly occurring or worsening clinically notable ECG abnormalities will be summarized. The same approach as for notable laboratory values will be used to define a newly occurring notable QTc value and a worsening notable QTc value. Notable ECG values will be listed.

Notable criteria are:

- QTcF > 500 msec or
- increase from baseline > 60 msec

If the single ECG shows a QTcF > 500 ms (males or females), 2 additional ECG replicates should be recorded to confirm the safety findings and copies forwarded to the central ECG laboratory for assessment. The results from those triplicate ECGs will be averaged and analysed as one value for summary and notable tables.

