6.5.5 Electrocardiogram (ECG)

ECGs must be recorded according to the ECG investigator manual. The Fridericia QT correction formula (QTcF) should be used for clinical decisions.

Single 12 lead ECGs are collected with ECG machines supplied by the core laboratory at the visits indicated in [Table 6-1](#). The original ECGs, appropriately signed, must be collected and archived at the study site.

Each ECG tracing must be labeled with study number, subject initials, subject number, date and time, and filed in the study site source documents. If the single ECG shows a QTcF > 500 ms (males or females), 2 additional ECG replicates should be recorded under continued controlled environmental conditions (patient resting, no interfering procedures to ensure as much as possible stable heart rate) to confirm the safety findings and copies forwarded to the central ECG laboratory for assessment. Shortly after completion of the triplicate ECG recording, a PK sample should be drawn to allow for correlation of PK to the QT/QTc.

If needed clinically significant ECG findings at randomization (pre-dose) may be discussed with the sponsor before administration of study treatment. Clinically significant abnormalities must be recorded on the relevant section of the Medical history/Current medical conditions/AE eCRF page as appropriate.

Detailed instructions concerning the ECG recording will be provided to all Investigators in a separate manual prior to the start of the study.

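### QTcF replicates are averaged only after a reading above 500 ms, so averaging can take an ECG out of the notable table but cannot put one in

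*SAP*

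**What the plan says.** Protocol 6.5.5 sets the routine measurement: "Single 12 lead ECGs are collected with ECG machines supplied by the core laboratory at the visits indicated in" Table 6-1. In that table, post-baseline ECGs fall at Weeks 4, 8, 12 and 13 and at the treatment discontinuation visit.

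The replicate trigger is the same in the protocol and the SAP: "If the single ECG shows a QTcF > 500 ms (males or females), 2 additional ECG replicates should be recorded". The protocol gives the purpose as "to confirm the safety findings and copies forwarded to the central ECG laboratory for assessment".

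SAP 2.8.4.1 then sets the analysis value: "The results from those triplicate ECGs will be averaged and analysed as one value for summary and notable tables". There are two notable criteria, "QTcF > 500 msec or" "increase from baseline > 60 msec", and the table reports newly occurring or worsening abnormalities, defined as for laboratory values in SAP 2.8.3. There, a patient counts if a notable value occurs at any visit after baseline. On listings the SAP says only "Notable ECG values will be listed".

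SAP section 4 adds: "Apart from analyses of clinical abnormalities summaries of laboratory data, vital signs and ECG intervals have been removed". Protocol 9.5.2.5 asks for the incidence of notable ECG abnormalities and gives no averaging rule.

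**The concern.** The trigger for replicates is the same cut-off as the first notable criterion, so a repeat is taken only when the first reading is already notable. A first reading above 500 ms may be pulled down by its replicates. A first reading at or below 500 ms is never repeated, so one that is too low by chance is never corrected upward.

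Patients are also classified on different measurements. The rise from baseline is judged on a mean of three for triggered ECGs and on one tracing for all others. A patient with the higher first reading can drop out of the count while a patient with a lower single reading stays in.

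This matters because the ECG interval summaries have been removed. The notable table and the notable listing are what remain of the planned ECG reporting, and with 129 patients randomized a single reclassified patient is visible.

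**Working it through.** The plan states no figure on this point, so there is none to reproduce. I applied the SAP rule directly.

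**Rule.** Let X1 be the scheduled reading, X2 and X3 the replicates, and B the baseline.
- If X1 > 500, the analysed value is V = (X1 + X2 + X3)/3. Otherwise V = X1.
- The ECG is notable if V > 500 or V − B > 60.
- A triggered ECG is therefore not notable only if V ≤ min(500, B + 60).

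**Direction.** Every triggered ECG is already notable on X1, because X1 > 500. Averaging can leave it notable or remove it. An untriggered ECG is unchanged. So the set of notable post-baseline ECGs can only shrink. (On the > 60 ms criterion alone, a mean above X1 could add a hit, but that ECG was already notable at > 500 ms.)

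**Example at one baseline, B = 435 ms.**
- Patient 1: X1 = 505 (+70), which meets both criteria. Replicates are 488 and 487. V = (505 + 488 + 487)/3 = 1480/3 = 493.3, and 493.3 − 435 = +58.3. Neither criterion is met, so the ECG is not counted.
- Patient 2: X1 = 496, with no replicates. 496 − 435 = +61, so the ECG is counted.

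**Break-even.** A triggered ECG falls to 500 ms or below when its two replicates average (1500 − X1)/2 or less: 497.5 for X1 = 505, 495 for X1 = 510, 490 for X1 = 520.

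**Size.** The documents give no within-person variability for QTcF. I assumed an SD of 8-12 ms and independent normal readings around a fixed true value, and took B as the recorded baseline. I simulated 2 million triplets per setting. All shares are among triggered ECGs. The first share is P(V ≤ 500 | X1 > 500). The others are P(V ≤ min(500, B + 60) | X1 > 500), where the minimum is 500 for B ≥ 440, 495 for B = 435 and 490 for B = 430.

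| True QTcF | Mean ≤ 500 | Leaves table, B ≥ 440 | Leaves table, B = 435 | Leaves table, B = 430 |
|---|---|---|---|---|
| 498 ms | 40-45% | 40-45% | 8-14% | 0.4-3% |
| 502 ms | 19-22% | 19-22% | 2-6% | under 1% |

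The first two share columns are equal because a mean of 500 or less cannot exceed a baseline of 440 or more by over 60 ms. At lower baselines the > 60 ms criterion keeps many of these ECGs in.

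**The case against.** Confirmation is the declared purpose of the replicates, and a mean of three estimates QTcF better than one tracing. At a true 498 ms, ending below 500 ms is the correct classification; a count on first readings would label 40-43% of ECGs at that true value as above 500 ms. The rule is prespecified and the same in every arm. This stands: it is a reason to keep the confirmed count, not to replace it. It does not answer the one-sidedness, since readings just below the cut-off get no such check and the > 60 ms criterion is never confirmed for untriggered ECGs.

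The table counts patients, not ECGs. A sustained prolongation has several visits at which to be counted, so one averaged visit need not remove a patient. This also stands, and it means that the percentages above are not shares of patients lost.

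High readings have other routes into the report. Clinically significant ECG abnormalities must be recorded on the medical history or adverse event page, and copies of the triggered tracings go to the central laboratory. That softens the effect but depends on judgement and does not restore the numeric count.

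A reader might infer that a reading above 500 ms vanishes from the listing as well. The SAP does not say so: its averaging sentence covers tables, and the listing sentence is silent on whether individual readings or the mean appear. That is an ambiguity, not a stated loss. A reader might also connect the point with the termination under urgent safety measures. Nothing in the documents links those measures to QT; the potential risks named are allergic dermatitis, hepatic enzyme elevation and neutropenia.

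**Conclusion.** The point holds as a limited defect of tabulation. For post-baseline ECGs, the rule can remove triggered readings from the notable count and never adds one, and it can reverse the order of two patients with the same baseline. That follows from the text alone.

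The size rests on the assumed SD of 8-12 ms and depends strongly on baseline. The rates of 40-45% (true 498 ms) and 19-22% (true 502 ms) describe leaving the table only when baseline is 440 ms or higher. It would be wrong to read them as the share of patients removed in general.

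The documents do not report how many patients exceeded 500 ms, so the effect on the actual table may be nil. This is a worthwhile clarification, not a threat to the safety conclusions.

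**What to change.** In SAP 2.8.4.1, present two rows for each criterion (> 500 ms and rise > 60 ms):
- one based on the scheduled single ECG, the measurement that all patients have;
- one with triggered ECGs replaced by the triplicate mean, labelled as confirmed.

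State also that every individual reading of any triggered ECG is listed, alongside the mean.

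The cost is SAP wording and one extra row per criterion. No new data are needed and the ECG procedure does not change. The downside is that some unconfirmed readings are shown; comparison with the confirmed row identifies them.
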